  - *Pediatric Subjects:* Pediatric subjects ( $\geq 5$  years) will complete five self-report outcome measures (**PROMIS® Itch, PROMIS® Pain Interference, Children's Dermatology Life Quality Index (CDLQI), PROMIS® Anxiety, PROMIS® Depression**) on an iPad. All self-report measures can be completed with the assistance of their parent or guardian. All five self-report outcome measures can be completed in 20 minutes or less. Pediatric subjects  $< 5$  years will not complete any self-report measures on the iPad.
  - *Caregiver Subjects:* All caregivers will complete one self-report questionnaire about their child's sleep habits (**Children's Sleep Habits Questionnaire (CSHQ)**) and two self-report measures for caregiver burden (**Caregiver Burden Inventory (CBI)**) and quality of life (**Family Dermatology Life Quality Index (FDLQI)**) on an iPad. All self-report measures can be completed in 5 minutes.
- Pediatric subjects will complete a Pediatric Subject Reimbursement Form at the end of the Baseline Assessment. The pediatric subject will print their name, address, sign and date the form. The adult caregiver may help the child complete the form if he/she has difficulty writing. Pediatric subject  $\geq 5$  years must sign the form. Study personnel will give the pediatric subject a \$10 gift card after for the completion of this form for completion of the Baseline Assessment. For pediatric subjects  $< 5$  years, the adult caregiver will complete and sign the form. Study personnel will give the adult caregiver subject a \$10 gift card after for the completion of this form for completion of the Baseline Assessment.
- Study personnel will call the caregiver by phone during the Week 3 of treatment for adverse event monitoring of their child who is participating and on topical treatment. Study personnel will ask: 1) Has your child been able to use the topical treatment without any problems?; 2) Has your child experienced any burning from the topical treatment?; and 3) Has your child experienced any side effects or adverse reactions while using the topical treatment?. Study personnel will document the phone call in the Call Log. Adverse events will be documented on AE source doc.
- Study personnel will call the caregiver by phone at least 48 hours prior to the 6 Week Assessment to remind he/she of their upcoming appointment and to bring their tube of topical treatment with them to the appointment. Study personnel will also monitor for

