adverse events by asking: 1) Has your child been able to use the topical treatment without any problems?; 2) Has your child experienced any burning from the topical treatment?; and 3) Has your child experienced any side effects or adverse reactions while using the topical treatment?. Study personnel will document the phone call in the Call Log. Adverse events will be documented on AE source doc.

- **6 Week Assessment:**

- This assessment should occur 6 weeks ( $\pm 7$  days) after the start of topical treatment (i.e., after Baseline Assessment). This study visit may be performed by telemedicine (i.e., zoom visit) if deemed appropriate and preferred by physician and subject. All currently scheduled and enrolled subjects will be given the option to have a study visit performed by telemedicine or in clinic. Study personnel will contact the enrolled subjects with scheduled 6 week and 12 week study visits by phone to ask if the subject would prefer to keep their in clinic study visit or have the study visit by telemedicine (zoom visit). All visits will be scheduled at a convenient time for the subject.
- **Study personnel:** Trained study personnel (MD/NP) will perform EASI and ISGA for the severity of atopic dermatitis. Study personnel will also weigh the tube of crisaborole and tacrolimus 0.03% prior to distribution to the subject. Study personnel will enter the EASI, ISGA, and tube weight into the electronic **Assessment Form (6 Week)** in REDCap.
- **Pediatric Subjects:** Pediatric subjects  $\geq 5$  years will complete five self-report outcome measures (**PROMIS® Itch, PROMIS® Pain Interference, Children’s Dermatology Life Quality Index (CDLQI), PROMIS® Anxiety, PROMIS® Depression**) on an iPad. All self-report measures can be completed with the assistance of their parent or guardian. All five self-report outcome measures can be completed in 20 minutes or less. Pediatric subjects  $<5$  years will not complete any self-report measures on the iPad.
- **Caregiver Subjects:** All caregivers will complete one self-report questionnaire about their child’s sleep habits (**Children’s Sleep Habits Questionnaire (CSHQ)**) and two self-report measures for caregiver burden (**Caregiver Burden Inventory (CBI)**) and quality of life (**Family Dermatology Life Quality Index (FDLQI)**) on an iPad. All self-report measures can be completed in 5 minutes.

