- Pediatric subjects will complete a Pediatric Subject Reimbursement Form at the end of the 6 Week Assessment. The pediatric subject will print their name, address, sign and date the form. The adult caregiver may help the child complete the form if he/she has difficulty writing. Pediatric subject  $\geq 5$  years must sign the form. Study personnel will give the pediatric subject a \$10 gift card after for the completion of this form for completion of the 6 Week Assessment. For pediatric subjects  $<5$  years, the adult caregiver will complete and sign the form. Study personnel will give the adult caregiver subject a \$10 gift card after for the completion of this form for completion of the Baseline Assessment.

- Study personnel will call the caregiver by phone during the Week 9 of treatment for adverse event monitoring of their child who is participating and on topical treatment. Study personnel will ask: 1) Has your child been able to use the topical treatment without any problems?; and 2) Has your child experienced any side effects or adverse reactions while using the topical treatment?. Study personnel will document the phone call in the Call Log. Adverse events will be documented on AE source doc.
- Study personnel will call the caregiver by phone at least 48 hours prior to the 6 Week Assessment to remind he/she of their upcoming appointment and to bring their tube of topical treatment with them to the appointment. Study personnel will also monitor for adverse events by asking: 1) Has your child been able to use the topical treatment without any problems?; and 2) Has your child experienced any side effects or adverse reactions while using the topical treatment?. Study personnel will document the phone call in the Call Log. Adverse events will be documented on AE source doc.
- **12 Week Assessment:**

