## **10. RISK/BENEFIT ASSESSMENT**

### **10.1. Potential Risks**

The proposed study is a low risk clinical trial. Subjects (patients & caregivers) will be completing self-report questionnaires at three different regularly scheduled clinic visits. The two topical treatments in the study are FDA-approved and standard care for  $\leq$ moderate atopic dermatitis. Crisaborole is approved for use in ages 2 years and older. Known side effects to crisaborole include pain at the site of application. Tacrolimus 0.03% is approved for use in ages 2 to 15 years. Known side effects to tacrolimus 0.03% include burning sensation, stinging, soreness, or pruritus at the site of application. These localized symptoms may occur during the first few days of use and subside as atopic dermatitis lesions improve. Subjects using tacrolimus should limit sun exposure and should not use ultraviolet light therapy, sun lamps, or tanning beds. Tacrolimus-treated skin should not be covered with bandages, dressings, or wraps. Contact of tacrolimus with eyes or mouth should be avoided. Unexpected side effects, such as allergic reactions, may occur and are unpredictable. This reaction may be mild, such as a skin rash, or you may have more severe symptoms like swelling of the throat, low blood pressure, and shortness of breath. If any of these unexpected side effects occur, subjects will be advised to stop use of their intervention immediately. Subjects will be informed about any additional potential risks if they are discovered. Furthermore, while we make every effort to keep all data and study information private, this cannot be guaranteed. All data will be de-identified and stored in a locked file in a locked office. All appropriate procedures will be taken to maintain subject privacy and data collected during this study.

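### The direct question about burning is asked at the first two safety calls but not at the last two, so burning that starts or persists after Week 6 may be under-recorded

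*Combined protocol and SAP*

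**What the plan says.** Sections 5.3 (Call Log) and 9.1 schedule adverse-event calls at Weeks 3, 6, 9 and 12. Section 5.1 gives the script for each.

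- The first call takes place "during the Week 3 of treatment for adverse event monitoring". It and the reminder call before the six-week visit each have three questions. After a question on problem-free use, both continue: "2) Has your child experienced any burning from the topical treatment?; and 3) Has your child experienced any side effects or adverse reactions".
- The third call is introduced with "Study personnel will call the caregiver by phone during the Week 9 of treatment for adverse event monitoring of their child". It and the reminder call after it each have two questions. They ask whether the child could use the treatment "without any problems?; and 2) Has your child experienced any side effects or adverse reactions while using the topical treatment". The burning question is absent from both.

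On the reactions themselves, section 10.1 states: "Known side effects to crisaborole include pain at the site of application". For tacrolimus 0.03% it lists burning, stinging, soreness and itch at the application site, and then adds: "These localized symptoms may occur during the first few days of use and subside as atopic dermatitis lesions improve".

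Section 9.2 also has staff record complaints that subjects volunteer. Section 9.3 has research staff review adverse reactions by treatment arm and send summaries to the Data Safety Monitoring Committee.

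**The concern.** Burning is a reaction the protocol itself names, and it is the only one asked about by name at any call. Halfway through a 12-week treatment period the plan stops asking about it directly and relies on general questions and volunteered complaints. A caregiver may say yes to a specific prompt and yet not mention the same symptom when asked about side effects in general. If so, late burning is recorded less completely than early burning.

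Two things are at stake. One is the completeness of the local-reaction record that goes to safety review for the second half of treatment. The other is how any by-visit table or sentence would be read: a fall in reported burning after Week 6 could be real, could come from the questioning, or could be both, and the data could not tell these apart.

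**Working it through.** There is no stated figure to reproduce. The check is a side-by-side reading of the four scripts in section 5.1.

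| Call | Questions | Direct burning question |
|---|---|---|
| Week 3 | 3 | yes |
| Before the six-week visit | 3 | yes |
| Week 9 | 2 | no |
| Call after Week 9 | 2 | no |

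The direct question is asked at 2 of 4 calls. The part of treatment without it runs from Week 6 to Week 12, which is 12 − 6 = 6 of 12 weeks.

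**Which visit the fourth call precedes.** It is printed as a reminder for the six-week visit. It comes after the Week 9 call and directly before the 12-week assessment, and sections 5.3 and 9.1 both list a Week 12 call. It is therefore the pre-Week 12 call with the wrong label. Read literally, the label would give the pre-Week 6 call two different scripts and leave Week 12 with no call. On either reading, no call after Week 6 asks about burning by name.

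**What can be lost.** Adverse events are recorded with a date of onset (sections 5.3, 9.1 and 9.2), so burning already reported at Week 3 or 6 stays on record. Two things remain exposed:

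1. Burning that first appears after Week 6. The ointment goes on all affected areas twice daily throughout (section 5.1), and subjects stay on assigned treatment during flares (section 8), so newly affected skin may first be treated late.
2. How long earlier burning lasted. Section 9.1 says the form holds a resolution date and duration. The field list for the AE Source Doc in section 5.3 has onset but no resolution date. If the form follows section 5.3, duration cannot be recovered from it.

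**Why a before-and-after comparison is confounded.** Let p1 and p2 be the true proportions with burning before and after Week 6, and d and g the fractions of cases captured by the direct and the general questions. Then

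recorded late / recorded early = (p2 / p1) × (g / d).

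The real change and the change in questioning enter as a product and cannot be separated. The second factor is 1 only if g = d.

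**Illustration for a table of reports by call.** The assumptions are not in the documents: true prevalence constant at 20%, and d = 1. Only the 40 evaluable children come from section 11.1. Expected reports at each early call are 40 × 0.20 × 1 = 8. At each late call they are 8 × g:

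| g | Expected reports |
|---|---|
| 0.25 | 2 |
| 0.50 | 4 |
| 0.75 | 6 |
| 1.00 | 8 |

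The range runs from no distortion to a large one, and the documents give no basis for choosing within it. The illustration does not apply to a count of children who ever had burning, because early reports are kept.

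**The case against.** The best defence is that the change of script is reasonable. Section 10.1 expects local symptoms in the first days of use, so asking directly early and generally later fits that expectation. This stands in part: some real fading is anticipated. It does not explain the script as written, because the plan still asks directly at Week 6, well past the first few days, and gives no reason for stopping there.

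A second defence is that other capture remains. Both later calls still ask about problems and about side effects, volunteered complaints are recorded, and clinicians assess the child at Weeks 6 and 12. Caregivers will also have heard the burning question twice. All of this is true, and capture could turn out equal. It is why under-recording is possible and not certain.

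A reader might go further and infer that burning will seem to fade purely because the question was dropped, and that the safety review in section 9.3 would show that fall. The documents do not support this. Section 9.3 describes a review by arm, not by time; section 11.2 plans no adverse-event analysis; and earlier reports are not erased.

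A reader might also infer a tilt between arms, since the prompted word is on the tacrolimus list while the crisaborole entry speaks of pain. The script is identical in both arms, the crisaborole entry is not worded as a complete list, and a caregiver could well describe such pain as burning. A tilt is possible but not shown, and no tolerability comparison is planned.

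**Conclusion.** The point holds as a minor flaw in safety data collection. The way a known local reaction is elicited changes midway through treatment, without explanation, at 2 of 4 calls. Burning that starts or persists after Week 6 may be under-recorded, and a comparison of local reactions before and after Week 6 would not be interpretable as a real change alone.

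This rests on one assumption: that general questions capture fewer cases than a direct one. If they capture the same, there is no effect. The documents do not allow the size to be estimated.

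The primary, secondary and tertiary outcomes are untouched. The consequence is limited to completeness of the safety record and to any by-visit reporting the investigators may choose to do. The documents do not establish that reported burning will fall, or that either arm is favoured. The wrong visit label on the fourth call is a separate, definite error.

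**What to change.** - Use the same question set at all four calls, in both arms. Include one direct question on burning, stinging or pain where the ointment is applied, so that the prompt covers terms listed for either product.
- Correct the visit label on the call after Week 9 so that it refers to the 12-week assessment.
- While editing, make the AE Source Doc fields in section 5.3 agree with section 9.1 on date of resolution, so that duration can be recovered.
- If some calls have already been made under the current script, state the change in questioning wherever local reactions are reported by visit.

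The cost is an edit to the call script and one extra question at two calls. No additional calls, visits or staff are needed.

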## 5.2. Topical Agent Distribution and Application

This is an open-label study using two topical treatments (crisaborole and tacrolimus 0.03%), which are both standard care topical treatments for  $\leq$ moderate atopic dermatitis:

- *Crisaborole*: Crisaborole is approved for atopic dermatitis in ages 2 years and older. Crisaborole will be provided to subject (provide by Pfizer) by study personnel in the clinic. Pfizer provided tubes of crisaborole for this study to avoid issues with non-coverage by medical insurances. The provided tubes of crisaborole will be stored at room temperature a locked cabinet in the CTU in University of Rochester Dermatology. A **Drug Accountability Record** will be kept with the crisaborole and completed each time a tube is dispensed to a subject. The Drug Accountability Record will record inventory and dispensing information. Inventory information will include: date received, number of tube, lot number, expiration date, staff initials, and balance. The Dispensing information will include: Subject ID, Date dispensed, number of tubes dispensed, lot number, balance forwarded, and staff initials. Study personnel will distribute the assigned tube of crisaborole to the subject at the Baseline Assessment. Study personnel will instruct the subject to apply the topical ointment to all affected areas twice daily throughout the study. Study personnel will instruct the subject to bring their tube of topical treatment with them to the 6 Week Assessment and the 12 Week Assessment for weighing.

*Expired or Unused Crisaborole*: The PI will monitor the expiration status of all crisaborole supplies and ensure that study subjects only receive crisaborole that is within its expiration date. The PI will provide Pfizer with sufficient notice (as defined by the mutual agreement of both parties before study initiation) if resupply is needed because of

pending expiration of existing supplies. Unless otherwise instructed by Pfizer in writing, Rochester will destroy any crisaborole supplies that expire during the study, as well as unused product at the termination of the study and agreement. Rochester will destroy these materials in accordance with applicable law and institutional policies.

- Tacrolimus 0.03%: Tacrolimus 0.03% is approved for atopic dermatitis in ages 2 to 15 years. Tacrolimus 0.03% will be provided to subject by study personnel in the clinic. Tacrolimus 0.03% will be purchased through the Investigational Drug Pharmacy at URMC as part of this study in order to provide the medication to subjects. Since this is an open-label study, the topical treatments will not be in matching tubes. Study personnel will instruct the subject to apply the topical ointment to all affected areas twice daily throughout the study. Study personnel will instruct the subject to bring their tube of topical treatment with them to the 6 Week Assessment and the 12 Week Assessment for weighing.

Expired or Unused Tacrolimus: The PI will monitor the expiration status of all Tacrolimus supplies and ensure that study subjects only receive tacrolimus 0.03% that is within its expiration date. The PI will provide the Investigation Drug Pharmacy with sufficient notice (as defined by the mutual agreement of both parties) if resupply is needed because of pending expiration of existing supplies. Unless otherwise instructed by the Investigational Drug Pharmacy, study personnel will destroy any tacrolimus supplies that expire during the study. The PI will return any non-expired, unused product to the Investigational Drug Pharmacy at the termination of the study and agreement. Rochester will destroy these materials in accordance with applicable law and institutional policies.

### 5.3. Outcome Measures and Study Forms

Eczema Area & Severity Index (EASI): The EASI is a tool used to measure the extent (area) and severity of AD. It does not include a grade for dryness or scaling and includes only inflamed areas (9). Area score is recorded for four regions of the body (head and neck, trunk including genital area, upper limbs, and lower limbs including buttocks). For head and neck region, the face occupies 33% (17% each side), the neck 33% (17% front and back), and the scalp occupies 33%. For the trunk region, the front occupies 55% and back 45%. For the upper limbs region, each arm occupies 50%, with the front or back of one arm equal to 25%. For the lower limbs region, each leg occupies 45%, with the front or back of one leg equal to 22.5% and the buttocks occupies 10%. The area score is the percentage of skin affected by AD for each body region. The **area score** is a 7-point scale representing the percentage of skin affected by AD for each body region (e.g., 0 = None; 1 = 1-9%; 2 = 10-29%; 3 = 30-49%; 4 = 50-69%; 5 = 70-89%; and 6 = 90-100%. The **severity score** is recorded for each of the four regions of the body and is the sum of the intensity scores for four signs. The four signs include redness, thickness, scratching, and lichenification. The intensity scores are performed using a 4-point scale (e.g., 0 = None, 1 = Mild, 2 = Moderate, and 3 = Severe). A severity score is the sum of the intensity scores for the four signs. For each body region, the severity score is multiplied by the area score and by a multiplier:

- Head and neck: severity score x area score x 0.1 (in children 0–7 years, x 0.2)
- Trunk: severity score x area score x 0.3
- Upper limbs: severity score x area score x 0.2

- Lower limbs: severity score x area score x 0.4 (in children 0–7 years, x 0.3)

The final EASI score is the sum of the total scores for each region. Add up the total scores for each region to determine the final EASI score. The minimum EASI score is 0 and the maximum EASI score is 72.

***Investigator Static Global Assessment (ISGA):*** The ISGA, a five-point global static assessment of AD severity, will be used to characterize subjects' overall disease severity across all treatable AD lesions (Table 1) (10). Training on how to assess the ISGA will be provided by [name]. Each ISGA assessment during the study must be done by trained study personnel.

**Tabel 1: Investigator's Static Global Assessment**

Score	Grade	Definition
0	Clear	Minor residual discoloration; no erythema or induration/papulation; no oozing/crusting
1	Almost Clear	Trace faint pink erythema, with barely perceptible induration/papulation and no oozing/crusting
2	Mild	Faint pink erythema with mild induration/papulation and no oozing/crusting
3	Moderate	Pink-red erythema with moderate induration/papulation with or without oozing/crusting
4	Severe	Deep or bright red erythema with severe induration/papulation and with oozing/crusting

***Percentage Body Surface Area (%BSA):*** The %BSA will be calculated by trained study personnel using the “rule of 9’s” (11). This method assigns percentages for body areas. In children the percentages are: Head & Neck = 9% (4.5% front or back); Chest = 18%; Back = 18%; Right arm = 9% (4.5% front or back); Hands = 2% (1% front or back); genitals = 1%; Right leg (including foot) = 18% (9% front or back); Left leg (including foot) = 18% (9% front or back).

***PROMIS® Itch (Pediatric):*** PROMIS® is the patient reported outcome measurement information system developed and validated by NIH and consists of domain-specific, but not disease-specific, measures within physical, mental and social health. PROMIS® Itch is a newly validated 8-item short-form spanning four domains (general, activity, mood/sleep, and scratching behavior). Each item is scored on a scale of 1 to 5. This PRO will be completed on an iPad and data will be submitted directly to the secure RedCap database at the University of Rochester Medical Center. This measure was created by [name] at Northwestern University. We have a DUA in place with [name] to use the Pediatric PROMIS Itch Short-form in this study. We will share de-identified data collected during this study with [name] to assist in further validation of the Pediatric PROMIS® Itch Short-Form. Unlike, the other PROMIS measures used in this protocol, the PROMIS Itch measure will not be automatically scored due to its novelty. It will be scored during data analyses using the appropriate conversion tables provided by [name].

PROMIS® Pain Interference (Pediatric): PROMIS® Pain Interference is a computer adaptive test (CAT) consisting of 4-12 questions related to how pain interferes with daily activities. The number of questions a patient answers depends on how he or she answers each question. A domain score of 50 is the average score for the general population. A score above 55 is considered “clinically significant” for each domain (12, 13). A score change of 5 or more is considered a clinically important change in domain severity (12, 13). This measure will be completed electronically on an iPad and data will be submitted directly to the secure RedCap database at the University of Rochester Medical Center.

PROMIS® Anxiety and Depression (Pediatric): These PROs will be completed electronically on an iPad. These domains are secondary outcome measures and are CAT domain consisting of 4-12 questions on feelings related to anxiety or depression. The number of questions a patient answers depends on how he or she answers each question. A domain score of 50 is the average score for the general population. A score above 55 is considered “clinically significant” for each domain (12, 13). A score change of 5 or more is considered a clinically important change in domain severity (12, 13). These two measures will be completed electronically on an iPad and data will be submitted directly to the secure RedCap database at the University of Rochester Medical Center.

Children’s Dermatology Life Quality Index: This PRO will be completed using an iPad. The 10-item questionnaire designed for use in parents of children (i.e., ages 4-17) to obtain information on children’s quality of life (14, 15). It is self-explanatory and can be simply handed to the patient who is asked to fill it in with the help of the child’s parent or guardian. Each question relates to a component of quality of life: Symptoms/Feelings (items 1-2); Leisure (items 4-6); School (item 7); Relationships (items 3-8); Sleep (item 9), and Treatment (item 10). Children answer each question using a 4-point scale: Not at all = 0, A Little = 1, Quite A Lot = 2, Very Much = 3. The scores from each item are summed to create a severity burden score (i.e., maximum score = 30). The scores represent degree of severity burden on quality of life: No effect = 0-1; Small effect = 2-6; Moderate effect = 7-12; Very large effect = 13-18; and Extremely large effect = 19-30. This measure will be completed electronically on an iPad and data will be submitted directly to the secure RedCap database at the University of Rochester Medical Center.

Children’s Sleep Habits Questionnaire (CSHQ): This PRO will be completed using an iPad. This is a validated and abbreviated form of the original CSHQ containing 22 items instead of 45 items (16, 17). This abbreviated CSHQ questionnaire consists of 4 subscales: Bedtime, Sleep Behavior, Waking During the Night, and Morning Wake Up. The patient/parent will answer each item choosing from: “Always” if something occurs every night; “Usually” if it occurs 5 or 6 times a week; “Sometimes” if it occurs 2 to 4 times a week; “Rarely” if it occurs once a week; and “Never” if it occurs less than once a week. Each question is scored on a 3-point scale as 1 = Usually and Always (5-7 times/week); 2 = Sometimes” (2-4 times/week); or 3 = Rarely and Never (0-1 time/week). The scores are combined from each subscale to generate a Total Sleep Disturbance Score, which can range from 22 to 66. A Total Sleep Disturbances score over 28 represent clinically significant sleep disturbance. This measure will be completed electronically on an iPad and data will be submitted directly to the secure RedCap database at the University of Rochester Medical Center.

*Caregiver Burden Inventory (CBI)*: The CBI is a 24-item, five-subscale Caregiver Burden Inventory (CBI) and demonstrates its use as a diagnostic tool for caregiver burden (18-20). The five subscales include: Time Dependency, Development, Physical Health, Emotional Health, and Social Relationships. Each subscale contains 4-5 items which are statements of feelings. Caregivers use a 5-point scale, anchored by “0” = “Never” and “4” = “Nearly Always”, to show how often the statement describes his/her feelings. Overall scores can range from 0 to 96, where a score near or above 36 indicates significant burden. All subscales have a maximum score of 20, except Physical Health which has a maximum score of 16. Subscale scores and item scores help identify the underlying cause of caregiver burden. This measure will be completed electronically on an iPad and data will be submitted directly to the secure RedCap database at the University of Rochester Medical Center.

*Family Dermatology Life Quality Index (FDLQI)*: The FDLQI is a 10-item questionnaire designed for adult family members of a patient with a skin disease (21, 22). It measures the impact of the patient’s skin disease on the family member’s quality of life. The caregiver will answer each question using a 4-point scale: Not at all = 0, A Little = 1, Quite A Lot = 2, Very Much = 3. The scores from each item are summed to create a severity burden score (i.e., maximum score = 30). The scores represent degree of severity burden on quality of life: No effect = 0-1; Small effect = 2-6; Moderate effect = 7-12; Very large effect = 13-18; and Extremely large effect = 19-30. This measure will be completed electronically on an iPad and data will be submitted directly to the secure RedCap database at the University of Rochester Medical Center.

*Screening Log*: This electronic form (REDCap) will be used to document the eligibility of subjects, if the subject consented or declined participation, and reason for declining participation. The Screening Log will help create a CONSORT diagram at the completion of the study. This form will electronically capture screening information for the study and submit the information directly to the secure RedCap database at the University of Rochester Medical Center. Study personnel will access the form electronically through a specific URL link.

*Eligibility Checklist*: This form contains the inclusion and exclusion criteria for participation in this study. This form is completed to ensure eligibility for the trial. Study personnel obtaining assent/consent will complete this form.

*Study Reimbursement Form*: This form is required along with a signed W9 for reimbursement of the adult caregiver in this study. The address on this form must match the signed W9 completed by the subject at the start of the study. After the assent/consent process is completed, the adult subject (i.e., Caregiver) will print their name, mailing address, sign, and date this form, as well as complete a W9 form. At the end of the subjects’ participation, the study coordinator or PI will circle the appropriate number of visits completed, indicate the number of visits completed, and indicate the amount to be reimbursed. A total of \$100 will be reimbursed for completion of all study procedures.

*Pediatric Subject Reimbursement Form*: This form is required at the end of each study visit to reimburse the pediatric subject with a \$10 gift card for completion of each visit (i.e., a total of

\$30 in gift cards). The address on this form must match the signed W9 completed by the subject at the start of the study. After completion of each study visit, the pediatric subject will print their name, mailing address, sign, and date this form. The adult caregiver may assist the pediatric subject with completion of this form; however the pediatric subject must sign the form. A \$10 gift card will be given to the pediatric subject after completion of this form.

*Call Log:* This is a password-protected excel spreadsheet that will contain contact information for the adult subjects. The spreadsheet contains Subject Pair ID, Caregiver Subject Name, Caregiver Subject Phone Number, and if voicemail can be left. The form will also capture each phone call made to the subject by study personnel. Study personnel will call the adult subject four different times during the study (i.e., Week 3, Week 6, Week 9, and Week 12) to screen for adverse reactions and reminders for study visits. Additional contact may occur to prevent loss to follow-up if subjects do not show up to an assessment or cancels their assessment appointments.

*Comprehensive Study Log:* This is a password-protected excel spreadsheet that contains a log for all subjects in the study. The information kept in this file include: Subject Pair ID, Caregiver Name, AD Patient Name, AD Patient MRN, Screened & Eligible, Assent Completed, Consent Completed, Screen Fail, Baseline Complete, 6 Week Complete, 12 Week Complete, Completed Study, Withdrawal, Loss to Follow-up, and Topical Treatment. Study personnel will complete the required subject information and check the appropriate boxes as the study progresses to monitor subject participation in the study.

*ASPIRE On-Study Form:* This form captures demographic information on both the caregiver and patient subjects, as well as relevant clinical information for the patient subjects. This form will be completed electronically and submit information directly to the secure REDCap database at the University of Rochester Medical Center. This form will collect the following:

- Subject Pair ID
- On Study Date
- Washout Period Required (yes/no)
- Caregiver Initials
- Relation of Caregiver
- Caregiver Gender
- Caregiver Age
- Caregiver Race
- Caregiver Ethnicity
- AD Patient Initials
- AD Patient Gender
- AD Patient Race
- AD Patient Ethnicity
- AD Patient Medical History
- AD Patient Current/Previous Treatments for AD
- AD Patient All Current Medications

Assessment Forms: These forms capture the EASI score, ISGA score, %BSA score, and topical treatment tube weight at each assessment (Baseline, 6 Week Assessment, and 12 Week Assessment). These forms will be completed electronically in REDCap during each specified assessment.

Withdrawal Form: This electronic form (REDCap) will be used to document the time and reasons for withdrawals during the study. This form will electronically capture withdrawal information for the study and submit the information directly to a secure REDCap database at the University of Rochester Medical Center.

AD Flare Medication Form: This electronic form (REDCap) will be used to document any extra medication prescribed to control an atopic dermatitis flare in a study subject. Study personnel will record the name of medication, dosage, date started, date ended, and continued for remainder of study (yes/no) for the extra medication. Subjects will remain on study unless he/she has is prescribed systemic anti-inflammatory therapy for atopic dermatitis. The treating dermatologist will manage and monitor the flare at their discretion.

AE Source Doc: This REDCap form will be completed by study personnel electronically (or on paper) to document any adverse reaction reported during the study. The form will record a description of the adverse event, date of onset, Serious (Yes/No), Intensity (Mild/Moderate/Severe), Relation to Study Drug (Definite/Probable/Possible/Unlikely/Unrelated), Action with Study Drug (No Action/Interrupted/Stopped Entirely).

Drug Accountability Record: This is a paper form that will be kept with the stock of tubes of crisaborole and tacrolimus 0.03% in a locked cabinet in the CTU in [REDACTED]. This form will record: the number of tubes in stock, the dispense date of the tube, Subject Pair ID for the tube, initials of study personnel, number of tubes dispensed, and adjusted number of tubes in stock. This form will be completed each time a tube of crisaborole or tacrolimus 0.03% is dispensed to a study subject.

